## **2.7.4 Other safety data**

### **2.7.4.1 ECG and cardiac imaging data**

PR, QRS, QT, QTcF, RR intervals and Mean heart rate (HR) will be obtained from 12-lead ECGs for each participant during the study. CCI

Categorical analysis of QT and QTcF interval data based on the number of participants meeting or exceeding predefined limits in terms of absolute QT/QTcF intervals or changes from baseline will be presented. This categorical analysis will be based on post-baseline visits. In addition, a listing of these participants will be produced by treatment groups.

- QT, QTcF
  - Absolute value of > 450 and ≤ 480 ms
  - Absolute value of > 480 and ≤ 500 ms
  - Absolute value of > 500 ms
  - Increase from baseline by > 30 ms to ≤ 60 ms
  - Increase from baseline by > 60 ms
- PR
  - Increase from baseline by >25% and to a value > 200 ms
  - Absolute value of > 200 ms and ≤ 220ms
  - Absolute value of > 220 ms
- QRS
  - Increase from baseline by >25% and to a value > 110 ms
  - Absolute values of QRS > 110 ms and ≤ 120ms
  - Absolute values of QRS > 120

- HR
  - Increase from baseline by >25% and to a value > 100 bpm
  - Decrease from baseline by >25% and to a value < 50 bpm

All ECG data will be listed by treatment group, participant, and visit/time; abnormalities will be summarized and flagged based on the criteria above. All ECG data will be summarized by treatment group and visit/time. A box plot will also be created for ECG parameters over time by treatment groups. For each treatment group, individual participant spaghetti plots will also be created for ECG parameters.

#### 2.7.4.2 Vital signs

All vital signs data (including Oxygen Saturation) will be listed and summarized by treatment group and visit/time and if ranges are available, abnormalities (defined below) and relevant orthostatic changes (if collected) and notable criteria (defined below) will be flagged in listing. Summary statistics will be provided by treatment group and visit/time for raw and change from baseline. Spaghetti plot will be created for all vital signs parameters except body weight.

Notable criteria (High/Low):

- Systolic blood pressure [mmHg]: >140/<90 mmHg
- Diastolic blood pressure [mmHg]: >90/<50 mmHg
- Pulse rate [bpm]: >90/<45 bpm
- Weight [kg]: >120/<50 kg
- Temperature [°C]: >37.5/<35 °C

#### 2.7.4.3

CCI

CCI

CCI

2.7.4.4

CCI

CCI

#### **2.7.4.5 Surgery related information**

All surgery related details will be listed by treatment group using the safety analysis set.

Descriptive statistics will be provided for the duration of cardiopulmonary bypass (hours), duration of surgery (hours), duration of total mechanical ventilation (hours), duration of pre-surgery mechanical ventilation (hours) and duration of post-surgery mechanical ventilation (hours).

Counts and percentages of the below combination of surgeries will also be summarized by treatment group:

CCI

CCI

2.7.4.6

CCI

2.8

CCI

CCI

**Table 2-1**

**CCI**

**CCI**

**2.8.1**

**CCI**

**CCI**

## 2.9 Immunogenicity

The analysis will be performed based on the IG analysis set.

Immunogenicity results will be listed by treatment group, participant and visit/time. The listing will contain ADA status (negative or positive) and for ADA-positive samples a titer CCI [REDACTED]. Participants with one or more treatment emergent ADAs are counted as ADA-positive participants and they will be summarized by treatment group to derive an ADA incidence. Treatment emergent ADAs are defined as induced or boosted ADAs developed after the treatment with TIN816. The ADA incidence will be provided by overall population, indicating the number and percentage of participants with treatment emergent ADAs at any time post-dose, compared with the total number of participants in the analysis set who received TIN816. CCI [REDACTED]

The proportion of participants with presence or absence of CCI [REDACTED] will be summarized by treatment and visit and listed by treatment, participant and visit.

A proper determination of ADA status of a participant is not possible if there are no post-dose ADA samples accessible for analysis. In that case, the pre-dose sample is analyzed in a three-tiered approach, but neutralizing ADA characterization assays are not performed.

CCI [REDACTED]

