8.9 Immunogenicity assessments

Immunogenicity (IG, production of anti-TIN816 antibodies) serum samples will be obtained and evaluated in all participants at all dose levels including the placebo group as defined in the assessment schedule ([Section 1.3](#)). Unscheduled ADA samples may be collected in case of a safety event ([Section 8.4](#)) that is potentially immunogenicity related. In case of suspected allergic hypersensitivity, the participant should return to the site and a sample to assess immunogenicity will be collected. Additionally, serum samples should be collected at the final visit from participants who discontinued study treatment or were withdrawn from the study. Details on immunogenicity serum sample collection, numbering, processing and shipment are provided in the Laboratory Manual.

Immunogenicity will be evaluated in serum by a validated three-tiered ligand binding assay approach (MSD bridging assay), details will be outlined in the method validation report.

All samples will be screened for potential anti-TIN816 antibodies. Any positive screen result is confirmed using a confirmatory assay where sample screening signal suppression upon addition of drug in excess is investigated. If a sample is confirmed positive for the presence of anti-TIN816 antibodies it will be further analyzed using a titration assay.

CCI

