### **2.1 Data analysis general information**

The final CSR analysis will be performed by Novartis.

SAS version 9.4 or later software will be used to perform all data analyses and to generate tables, figures and listings.

CCI

Data from TIN816 treatment groups (CCI) will not be pooled for the analyses and will be reported separately. All the placebo participants will be pooled for the analyses.

All inferential analyses will use 1-sided tests, 0.1 significance level and 90% confidence

CCI

Categorical data will be presented as frequencies and percentages. For continuous data, mean, standard deviation, median, minimum, and maximum will be presented. For selected parameters, 25th and 75th percentiles will also be presented.

CCI

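### SAP 2.9 ties treatment-emergent ADA to TIN816, which conflicts with its own by-group ADA summary and leaves no usable placebo incidence; its overall figure also combines two doses that SAP 2.1 keeps apart

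*SAP*

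**What the plan says.** **How ADA positivity is counted.** SAP 2.9 treats participants with at least one treatment-emergent ADA as ADA-positive and says "they will be summarized by treatment group to derive an ADA incidence". It then defines the term: "Treatment emergent ADAs are defined as induced or boosted ADAs developed after the treatment with TIN816". Protocol 9.4.3 has the same counting rule by treatment group, and its visible text has no limit to TIN816.

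**The overall figure.** SAP 2.9 then adds a single incidence: "The ADA incidence will be provided by overall population". It counts anyone with such an ADA at some point after dosing, and the denominator leaves placebo out: "compared with the total number of participants in the analysis set who received TIN816".

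**Pooling.** SAP 2.1 says of the TIN816 dose groups that their data "will not be pooled for the analyses and will be reported separately", while all placebo participants are pooled. Protocol 9.2.1 has the same rule for the TIN816 groups.

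**What is collected on placebo.** Under Protocol 8.9, immunogenicity samples are "evaluated in all participants at all dose levels including the placebo group as defined in the assessment schedule". The immunogenicity set (SAP 2.2) is open to recipients of any study treatment, and SAP 2.1.1 counts placebo as study treatment. The immunogenicity baseline is the pre-surgery sample (SAP 2.1.1). The schedule in Protocol 1.3 has post-dose samples at Days 8, 30 and 90. SAP 2.9 also says: "Immunogenicity results will be listed by treatment group, participant and visit/time".

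**The concern.** Two instructions in one paragraph cannot both be followed to a meaningful result. A summary by treatment group needs a rule that can be applied in every group. The definition makes prior TIN816 exposure part of the event itself, so no placebo participant can meet it.

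The placebo arm is the concurrent control for conversions that arise after the pre-surgery sample for reasons other than the drug. If its incidence is printed as zero, a reader may take that as an observed result when it is only a consequence of the definition. All background conversion on TIN816 would then look like drug effect. If the cell is left blank, the TIN816 incidence has nothing beside it. Either way, someone must decide how to count placebo conversions, and that is better settled before treatment codes are open. Immunogenicity is a named secondary objective.

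The second issue is smaller. An overall incidence over all TIN816 recipients depends on how many were enrolled at each dose, and the SAP says elsewhere that the doses are not combined.

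**Working it through.** The documents state no ADA rate, assay cut-point or precision target, so there is no figure to reproduce. The check is mainly a comparison of text. The arithmetic only illustrates size.

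**1. Apply the definition to a placebo participant.** Take someone negative pre-surgery and confirmed positive at Day 30.
- In the immunogenicity set? Yes, as a recipient of study treatment (SAP 2.2, 2.1.1).
- In the by-group summary? Yes, placebo is a treatment group.
- Induced relative to baseline? Yes.
- After treatment with TIN816? No, so not treatment-emergent and not ADA-positive.

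Every placebo participant fails at the last step, whatever the assay shows. For comparison, SAP 2.7.1 defines treatment-emergent adverse events from Day 1 for all groups alike.

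**2. Set the overall figure against SAP 2.1.** Its denominator is all TIN816 recipients in the set, so it combines two dose groups. The visible text of 2.9 does not mark this as an exception.

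**3. Size of a background rate (assumed).** Let f be the chance that one post-dose sample is positive without drug effect. With three post-dose samples, assumed independent, the chance of at least one positive is 1 − (1 − f)³.

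| f (assumed) | 1 − (1 − f)³ | Expected in 40 | Expected in 80 |
|---|---|---|---|
| 0.1% | 0.3% | 0.12 | 0.24 |
| 1% | 3.0% | 1.2 | 2.4 |
| 2% | 5.9% | 2.4 | 4.7 |
| 5% | 14.3% | 5.7 | 11.4 |

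The group sizes are assumptions because the allocation ratio is redacted. Positive correlation between a participant's samples lowers the any-time rate; with complete correlation it falls to f itself.

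**4. What placebo could show.** With no positives among n placebo participants, the one-sided 95% upper bound on the background rate is 1 − 0.05^(1/n): 9.5% for n = 30, 7.2% for n = 40 and 4.9% for n = 60.

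**5. Effect of combining doses (assumed rates of 5% and 20%, 80 recipients).**
- 60 and 20: (60 × 0.05 + 20 × 0.20)/80 = 7/80 = 8.8%
- 40 and 40: (2 + 8)/80 = 12.5%
- 20 and 60: (1 + 12)/80 = 16.3%

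With the same two dose-level rates, the overall figure nearly doubles on enrolment split alone.

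**The case against.** The defence has several sound parts.

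- **Dose-level incidence is planned.** A reader might infer that the SAP reports only a combined figure and hides any dose difference. It does not: the by-group summary stands, and the overall figure is an addition. What remains is an unreconciled exception to SAP 2.1.
- **Placebo results are not lost.** A reader might infer that the placebo samples yield no background information. ADA status is listed by group, participant and visit, so placebo conversions will be visible and can be counted. The gap is in the definition behind the summary.
- **Attribution is not impossible.** Induced or boosted implies comparison with the pre-surgery sample, and Protocol 8.9 requires a confirmatory step using suppression by excess drug. Both limit pre-existing and non-specific reactivity. Neither excludes conversion that arises after baseline, which is what a placebo rate would measure.
- **Redaction.** Parts of SAP 2.9 and Protocol 9.4.3 are blacked out and could contain a placebo summary or the induced and boosted criteria. It cannot be said that placebo reporting is absent. The visible definition still conflicts with the visible by-group plan.
- **Loose drafting.** The sponsor may intend the same rule for placebo, and no visible text says that 0% will be reported. That is a reason to correct the sentence.
- **Transfusion.** One might suggest antibody from transfused products as a source of background. Nothing in the documents says donor products carry antibody to TIN816, so the point does not rely on this.
- **Low stakes.** The trial is non-confirmatory, and the visible text shows no test or decision rule for ADA. This limits the severity.

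**Conclusion.** The concern holds as a conflict within SAP 2.9 and between SAP 2.9 and SAP 2.1. As worded, the treatment-emergent definition cannot be met on placebo, so the placebo entry in the planned by-group incidence is zero or undefined and the TIN816 incidence lacks its concurrent control. The overall incidence combines doses that the SAP says are not combined.

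The documents do not support the stronger conclusion that TIN816 incidence cannot be attributed to the drug, for the reasons given above.

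The size is uncertain. The figure of about 3–6% rests on an assumed 1–2% per-sample rate, three samples and independence. A much lower rate would make the issue negligible in numbers, and correlation would shrink it. The placebo estimate would also be imprecise, as the upper bounds show. The consequence is confined to interpreting a descriptive secondary endpoint; the primary creatinine analysis is untouched. The change is worth making because it corrects a stated rule using data already collected.

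**What to change.** In SAP 2.9:

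1. Define treatment-emergent ADA as induced or boosted relative to the pre-surgery sample, after administration of any study treatment (TIN816 or placebo).
2. Report the incidence side by side for pooled placebo and for each TIN816 dose, each with its own number of participants as denominator.
3. Drop the overall TIN816 incidence, or keep it labelled as supplementary and as an explicit exception to SAP 2.1.

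No transfusion listing is needed. If redacted text already covers placebo, the visible definition should be aligned with it.

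The cost is a wording change and a placebo column computed by the same rule. Placebo samples are already collected, evaluated and listed, so no new sampling or assay work is required. The change should be made before treatment codes are opened for the final analysis.

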10.5.1 Liver event and laboratory trigger definitions & follow-up requirements

Table 10-2 Liver event and laboratory trigger definitions

	Definition/ threshold
Liver laboratory triggers:	ALT or AST > 5 × ULN
If ALT, AST and total bilirubin normal at baseline:	
ALP > 2 × ULN (in the absence of known bone pathology)
 
Total bilirubin > 3 × ULN (in the absence of known Gilbert syndrome)
 
ALT or AST > 3 × ULN and INR > 1.5
 
Potential Hy's Law cases (defined as ALT or AST > 3 × ULN and Total bilirubin > 2 × ULN [mainly conjugated fraction] without notable increase in ALP to > 2 × ULN)
 
Any clinical event of jaundice (or equivalent term)
 
ALT or AST > 3 × ULN accompanied by (general) malaise, fatigue, abdominal pain, nausea, or vomiting, or rash with eosinophilia
 
Any adverse event potentially indicative of a liver toxicity

If ALT or AST abnormal at baseline:	ALT or AST > 3x baseline AND > 5x ULN

Table 10-3 Follow up requirements for liver laboratory triggers - ALT, AST, TBL

ALT	TBL	Liver Symptoms	Action
ALT increase without bilirubin increase:			
• No change to study treatment• Measure ALT, AST, ALP, GGT, TBIL, INR, albumin and CK in 48-72 hours.• Follow-up for symptoms.• Initiate close monitoring and workup for competing etiologies.
If normal at baseline: ALT > 5 x ULN for more than two weeks OR ALT > 8 x ULN	Normal For participants with Gilbert's syndrome: No change in baseline TBL	None	
If elevated at baseline: ALT > 3 x baseline AND > 5x ULN for more than two weeks OR ALT ≥ 5x baseline AND ≥ 8x ULN			
ALT increase with bilirubin increase:			
If normal at baseline: ALT > 3 x ULN	TBL > 2 x ULN (or INR > 1.5) For participants with Gilbert's syndrome: Doubling of direct bilirubin	None	
If elevated at baseline: ALT > 2 x baseline AND >3x ULN			
If normal at baseline: ALT > 3 x ULN	Normal or elevated*	Severe fatigue, nausea, vomiting, right upper quadrant pain*	
If elevated at baseline: ALT > 2 x baseline AND > 3x ULN			
* This situation suggests liver injury based on (i) elevation of ALT, and (ii) the presence of symptoms of liver injury. Even if bilirubin is normal, the presence of liver symptoms indicates potentially severe liver injury.			

Table 10-4 Follow up requirements for liver laboratory triggers - Isolated Hyperbilirubinemia

Criteria	Actions required	Follow-up monitoring
Total Bilirubin (isolated)		

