## 2.2 Analysis sets

For all analysis sets, participants will be analyzed according to the study treatment(s) received.

The safety analysis set will include all participants that received any study treatment (TIN816 or Placebo).

CCI

The PD analysis set will include all participants that received any study treatment and had no protocol deviations with relevant impact on PD data.

The IG analysis set will include all participants with at least one available valid (i.e. not flagged for exclusion) IG concentration measurement, who received any study treatment and with no protocol deviations that impact on IG data.

Additional details on the analysis set definitions are provided in [Table 5-3](#).

Participants with protocol deviations will be presented and listed for all participants in safety analysis set. The number of participants with protocol deviations will be tabulated by deviation category by treatment.

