### **2.7.1 Adverse events (AEs)**

All information obtained on adverse events will be listed by treatment group and participants.

All AE summary tables will be created for two periods: AEs which occurred only on Day 1, vs. AEs that occurred on and after Day 2 and end by Day 90 (EOS).

The treatment emergent adverse events (TEAEs) are defined as the events started from Day 1 or events present prior to start of Day 1 but increased in severity based on preferred term. The number and percentage of participants with TEAEs will be summarized in the following ways for both periods (defined above) and overall (from Day 1 to EOS):

- by treatment, primary system organ class and preferred term
- by treatment, primary system organ class, preferred term and maximum severity.

Separate summaries will be provided for study medication related adverse events, death, serious adverse events, and other significant adverse events leading to discontinuation, dose interrupted/withdrawn, and adverse events by severity class by period, treatment, primary system organ class and preferred term.

A participant with multiple adverse events within a primary system organ class is only counted once towards the total of the primary system organ class.

A 'Total' column will be shown for all AEs related summaries.

A similar separate summary will be created for non-serious adverse events accounting for >5% of all recorded adverse events by system organ class and preferred term.

All adverse events and serious adverse events will be listed by study day, treatment group and participant.

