#### **2.7.3 Laboratory data**

Some laboratory parameters were collected from both, local and central labs. In case of duplicate information, local lab results will be preferred over central labs.

All laboratory data (absolute, change from baseline and ratio to baseline) will be summarized by treatment group, and visit/time.

All laboratory data parameters (hematology, clinical chemistry, lipid panel, renal chemistry, urine chemistry, urine microscopy/sediment, urine dipstick, CCI hepatitis testing, and liver event/follow-up testing) will additionally be listed by treatment group, participant and visit/time, and if local normal ranges are available, then abnormalities will be flagged in the listing.

Below notable severe drug induced liver injury (including Hy's law) will be summarized using count and percentage by treatment group:

- ALT or AST > 5x ULN
- ALT or AST >3xULN
- ALT or AST >3x ULN and TBL >2x ULN
- ALT or AST >3xULN and INR >1.5xULN)

- ALP >2xULNALT or AST >3x ULN and TBL >2x ULN and ALP <2xULN (Hy's law cases).

A spaghetti plot and box plot will be created for all laboratory parameters over time by treatment group, with a line indicating the treatment group mean.

CCI

Another spaghetti plot will be generated for the liver monitoring parameters from liver monitoring visits and local/central lab, over study day, by treatment. In case of more than one record is available at a particular day, the highest value will be considered. The AKI stage 2 and stage 3 participants will be highlighted in the plot.

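### Three SAP counting rules can understate three specific summaries: the overall ADA incidence, the ALT/AST-with-INR row and the supplementary non-serious AE table

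*SAP*

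**What the plan says.** **ADA incidence.** SAP 2.9 first plans an ADA incidence by treatment group. It then adds an overall incidence, in which participants with treatment-emergent ADA are "compared with the total number of participants in the analysis set who received TIN816". To enter the IG analysis set (SAP 2.2, and likewise Protocol 9.1) a treated participant needs "at least one available valid (i.e. not flagged for exclusion) IG concentration measurement". No sampling time is required. The only ground for exclusion from that set listed in SAP Table 5-3 is the informed-consent deviation. Later in SAP 2.9 we read: "A proper determination of ADA status of a participant is not possible if there are no post-dose ADA samples accessible for analysis". The text goes on: "In that case, the pre-dose sample is analyzed in a three-tiered approach". Scheduled immunogenicity samples in the Protocol 1.3 schedule are pre-surgery, Day 8, Day 30 and Day 90. SAP 2.1 and Protocol 9.2.1 say that the two TIN816 dose groups are reported separately and not pooled.

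**Liver summary.** One row of the SAP 2.7.3 summary is "ALT or AST >3xULN and INR >1.5xULN". Protocol Table 10-2 defines the trigger as "ALT or AST > 3 × ULN and INR > 1.5", and Table 10-3 also uses INR above 1.5 with no ULN multiplier.

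**Non-serious AEs.** SAP 2.7.1 asks for a separate summary of "non-serious adverse events accounting for >5% of all recorded adverse events by system organ class and preferred term". The main treatment-emergent AE tables in the same section count participants and carry no frequency threshold.

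**The concern.** Each rule differs from what its table appears meant to show, and each can make a number smaller or a table shorter.

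- **ADA.** A participant whose status the SAP calls undeterminable can still sit in the denominator and can never reach the numerator. ADA is a secondary endpoint, so the headline percentage is affected.
- **INR.** The SAP row does not count the event that the protocol defines as a liver trigger. Because local laboratories are used (Protocol 8.4.5), its effective cut-off can also vary between sites.
- **AE threshold.** A cut-off set as a share of events rises with every unrelated event recorded. After bypass surgery the event total may be large. Read literally, the denominator includes serious events, while the terms listed are non-serious.

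**Working it through.** The documents give no figure for any of these rules, so there is nothing of the plan's own to reproduce. The sample-size text, allocation ratio and arm sizes are redacted. The inputs taken from the documents are the rules above and the planned total of about 120 participants. Every other input is an assumption, shown as a range.

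**1. ADA denominator.** Let N be the TIN816 recipients in the IG set, m those without a post-dose sample, u = m/N, and x the participants with treatment-emergent ADA.

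- SAP rate = x/N. Rate among evaluable participants = x/(N − m).
- Hence SAP rate = evaluable rate × (1 − u).
- For an evaluable rate of 20%:

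| u (assumed) | Reported |
|---|---|
| 2% | 0.20 × 0.98 = 19.6% |
| 5% | 0.20 × 0.95 = 19.0% |
| 10% | 0.20 × 0.90 = 18.0% |
| 20% | 0.20 × 0.80 = 16.0% |

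- In counts, with an assumed 6 positives and N = 60: 6/60 = 10.0% under the SAP rule, 6/57 = 10.5% if 3 are unevaluable, and 6/54 = 11.1% if 6 are.

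Relative to the evaluable rate, the shift is downward whenever u is above zero. With the first scheduled post-dose sample on Day 8, the likely contributors are deaths before Day 8 and missed samples.

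**2. INR criterion.** SAP cut-off = 1.5 × ULN; protocol cut-off = 1.5.

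| Local ULN (assumed) | SAP cut-off | Against 1.5 |
|---|---|---|
| 0.9 | 1.35 | counts more |
| 1.0 | 1.50 | same |
| 1.1 | 1.65 | counts fewer |
| 1.2 | 1.80 | counts fewer |
| 1.3 | 1.95 | counts fewer |

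The two rules agree only at a ULN of 1.0. At 1.1 to 1.3, an INR above 1.5 but not above 1.65 to 1.95 meets the protocol definition and is left out of the SAP row.

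**3. Non-serious AE threshold.** Let a be the mean number of recorded AEs per participant, with 120 participants. Under the SAP rule a term needs more than 0.05 × 120 × a = 6a events. A participant rule on the same base needs more than 0.05 × 120 = 6, that is 7 participants (5.8%).

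| a (assumed) | All events | Events needed | Share of 120 at one event each |
|---|---|---|---|
| 0.5 | 60 | 4 | 3.3% |
| 1 | 120 | 7 | 5.8% |
| 2 | 240 | 13 | 10.8% |
| 3 | 360 | 19 | 15.8% |
| 5 | 600 | 31 | 25.8% |
| 8 | 960 | 49 | 40.8% |

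At one event per affected participant, the rules cross at about a = 1. Above that the event-share rule is stricter; below it, the rule lists more terms. Because 0.05 × n × a equals 0.05 × n at a = 1 for any n, the crossing point does not depend on the redacted arm sizes. Repeated events of one term in the same person would reach the event threshold with fewer participants.

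**The case against.** A reader might infer that these rules under-report harm, or that a drug-specific excess could vanish from the report. The documents do not support that.

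- **AEs.** SAP 2.7.1 plans participant-level tables by system organ class and preferred term, by treatment, with no threshold. It adds serious, drug-related and severity tables and full listings. The share-of-events table is an extra.
- **Liver.** ALT or AST above 3 × ULN has its own row in SAP 2.7.3, so every case meeting the protocol's INR combination is already counted there. Laboratory values are listed. The protocol's follow-up triggers are untouched. The documents give no local ULN, so even the direction of the difference is unknown. SAP section 4, on changes to protocol-specified analyses, is redacted, so a declared change cannot be ruled out.
- **ADA.** Immunogenicity is not harm in itself. One might also infer that every early withdrawal is called ADA-negative. No visible text labels anyone so. Protocol 8.9 asks for a final-visit sample from participants who discontinue treatment or are withdrawn, so many of them should be evaluable. Incidence by treatment group is already planned, and the pooling conflict concerns only the overall figure. Redacted text follows both the denominator sentence and the evaluability paragraph, and could contain a condition. At u of 2% to 5%, the change from 20% is one percentage point or less.

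These points limit the consequences. What stands is that the visible ADA denominator conflicts with the SAP's own statement on evaluability, that the INR row differs from the protocol, and that one AE table uses a threshold that moves with the event total.

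**Conclusion.** The point holds in a limited form: three stated rules can understate three specific summaries.

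- **ADA is the firmest.** Subject to the redacted text, the visible rule can only lower the overall rate relative to evaluable participants, by the factor (1 − u). The size rests on an assumed u and is small if few samples are missing. Combining the two doses conflicts with SAP 2.1.
- **The INR mismatch is certain; its direction is not.** The SAP row is less sensitive only where the local ULN is above 1.0.
- **The AE rule is stricter than a participant rule only above about one recorded AE per participant.** More than that is plausible after this surgery, but it is an assumption.

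None of the three touches the primary analysis or participant management, and no safety signal is lost from the report as a whole. The corrections are still worth making, because they concern stated rules and cost very little.

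**What to change.** Three edits to the SAP, with no new data collection:

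1. **SAP 2.9.** Use as denominator the TIN816 participants with at least one evaluable post-dose ADA sample, and with a baseline sample where that is needed to classify ADA as induced or boosted. Report by dose group and show the number unevaluable in each. If the redacted text already contains such a condition, confirming it is enough.
2. **SAP 2.7.3.** Reconcile the INR row with Protocol Tables 10-2 and 10-3 so that it counts the trigger the protocol defines. This concerns what the table counts and takes no position on the clinical threshold. The separate ALT/AST row and the listings stay as they are.
3. **SAP 2.7.1.** Define the threshold as non-serious AEs occurring in more than 5% of participants in any treatment group.

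The cost is minor reprogramming. The ADA percentage may rise slightly. The non-serious AE table will be longer if AEs average more than about one per participant.
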